Aim 1: The study population will consist of 200 patients (100 control, 100 treated with Ketorolac) that are admitted to the inpatient surgical service at our level I trauma centers for management of orthopedic trauma care. All trauma patients that are between the ages of 18-75 and with NISS > 9 (moderate injury) [33, 34] will be enrolled and treated according to the standard Advance Trauma Life Support (ATLS) protocol. 100 patients in the control group will receive placebo intravenous saline every 6 hours for their initial 5 days of hospitalization and no NSAID administration. 100 patients randomized to the treatment group will receive 15 mg of Ketorolac every 6 hours for their initial 5 days of hospitalization. A daily blood sample (10 cc) will be collected on Days 1–5 by blinded health care personnel. These blood samples will be analyzed via sandwich ELISA method for concentrations of IL-1, IL-6, IL-10, and PGE2. Serum concentrations will be compared between the treatment and control groups using two-tailed independent t-tests. In addition to the standard trauma labs, patient demographics, injury data (gender, age, BMI, mechanism of injury, NISS, and types of surgical/procedural interventions), injury outcomes (incidence of bacterial pneumonia, ARDS, SIRS, MODS), complications defined in the National Trauma Dataset, and inflammatory data will be compiled, tracked, and maintained in our clinical database (REDCap). Outcome variables (hospital and ICU length of stay and occurrence of pneumonia and/or ARDS and/or SIRS or death), and the predictor variables of interest (inflammatory markers and NISS) will be compared using Poisson regression. The odds of developing post traumatic complications in the different predictor groups will be determined using multiple logistic regressions. The covariates will be adjusted for in the regression models: age, sex, injury severity, severity of head and/or extremity injury, injury mechanism, and injury outcome.

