Interventional Model Description: Compare the effectiveness of a NSAID to placebo in acute trauma setting.

Masking: Triple (Participant, Care Provider, Investigator)

Masking Description: Participant medical team will be blinded to the treatment or placebo intervention.

3. Outcome Measures

Primary Outcome: Length of Hospital Stay

Secondary Outcomes:

- Daily Concentrations of IL-1, IL-6, IL-10, and PGE2
- Incidence of Post-Traumatic Complications (e.g., bacterial pneumonia, SIRS, MODS, ARDS, and AKI)
- Mortality
- Visual Analogue Pain Scores
- Inpatient Morphine Milligram Equivalents
- Change in Inpatient Subjective Pain Reports
- Change in Outpatient Subjective Pain Reports

4. Background

Accidental trauma is the 4th leading cause of death in the United States, and it is associated with a complex inflammatory response. This response is associated with post-traumatic complications such as multi-organ dysfunction syndrome (MODS), bacterial pneumonia, acute respiratory distress syndrome (ARDS), systemic inflammatory response syndrome (SIRS), and post traumatic pain (PTP). It is unknown whether early modulation of inflammatory cytokines is associated with improved patient outcomes, reduced narcotic requirements, and improved patient subjective pain after hospital discharge.

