- k. Patients with chronic use of steroids or immune modulating drugs or history of organ transplantation
- l. Patients with preexisting chronic renal, liver, or lung disease
- m. Patients with history of myocardial infarctions
- n. Patients with chronic heart failure
- o. Patients with allergy to NSAID
- p. Patients with coagulation defects (e.g., clotting factor deficiencies, thrombophilia, or any bleeding disorder)
- q. Patients receiving chronic opioid therapy or treatment for opioid use disorder.

6. Sample Size Calculation

Pretrial sample size calculations were performed regarding LOS because this will be the primary outcome measure of the clinical trial. Using a significance level of 0.05 and an assumed SD of 1.5 days, a sample size of 42 patients per group (84 total) would yield 80% power to detect a difference of 0.928 days in average LOS between the placebo and ketorolac groups. Allowing for a dropout rate up to 25%, the target enrollment will be 112 patients total, with 56 patients per group. Power calculations were performed using nQuery 8.5 (Statistical Solutions Ltd; Cork, Ireland).

7. Statistical Analysis Plan

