Group-level summary statistics will be calculated for demographic and clinical variables, and differences between the 2 groups will be evaluated using two-sample t-tests for quantitative measures and Fisher exact tests for categorical measures, as appropriate. LOS and MME values will be summarized using medians and interquartile ranges for each group. Group-level VAS pain scores will be summarized using means and standard deviations. An analysis of variance model will be fit to compare log-transformed LOS between the 2 groups. Linear mixed models will be used to estimate differences in VAS pain scores and log-transformed MME values over time between the 2 groups. Time and group comparisons for each cytokine will be made using linear mixed models, with and without adjusting for selected covariates. Patient demographic variables will be considered for inclusion as covariates in each model but will only be retained if they significantly improve the model. Linear mixed models may be log-transformed, double-log-transformed, or square-root-transformed to correct for right skewness, as appropriate. Likelihood ratio testing and Akaike information criterion will be used to select appropriate covariance structures in each case. A Kenward–Roger adjustment will be used to correct for negative bias in the standard errors and degrees of freedom calculations. Throughout the study, a P value of less than 0.05 will be considered significant. All analyses will be completed in SAS 9.4 (SAS Institute Inc.; Cary, NC).

8. Study-Wide Recruitment Methods

Potential patients will be prospectively identified either at the time of the initial consultation, at the morning fracture conference, based on the orthopaedic injury diagnosis (inclusion criteria noted above). Patients will be screened by their inclusion and exclusion criteria and will be considered for enrollment in the study should they meet study criteria.

9. Study Timeline

After arrival, patient screening and enrollment is expected within 12 hours of arrival to ensure initial blood draw. Further participation of subjects will include blood draws and ketorolac administration through day 5. Patient participation will continue through to their follow-up visits and conclude with their 6 weeks post discharge clinic visit. Detailed project timeline and schedule of activities is listed in Table 1.

Tentative time table of the proposed project												
Procedures	Enrollment	Inpatient						Outpatient				

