		Day 1	Day 2	Day 3	Day 4	Day 5	Discharge	2 Week	6 Week	3 Month	6 Month	12 Month
Inclusion/Exclusion Review	X											
Informed Consent	X											
Blood Sample		X	X	X	X	X						
Ketorolac Intervention		X	X	X	X	X						
MME		X	X	X	X	X	X					
VAS		X	X	X	X	X	X	X	X	X	X	X
Post-Traumatic Complications		X	X	X	X	X	X	X	X	X	X	X

10. Procedures Involved

- Patient identification:** Patients will be identified on morning intake rounds by the trauma team and the research staff who are present daily to screen and enroll patients.
- Screening/Enrollment:** Study population will consist of 112 patients (56 control, 56 treatment) admitted to the inpatient surgical service at University of Kentucky (UK) level I trauma center for management of trauma care. Trauma patients that are between the ages of 18-75 and with NISS > 9 (moderate injury) with anticipated admission of ≥ 5 days (to ensure completion of the treatment) will be enrolled (Grisoni et al., 2001; Stevenson, Segui-Gomez, Lescohier, Di Scala, & McDonald-Smith, 2001). All patients will be initially treated according to the standard Advance Trauma Life Support (ATLS) protocol and standard ICU protocols (if applicable). Experienced clinical research staff will prospectively identify patients who meet the inclusion criteria and none of the exclusion criteria detailed in table 2.
- Randomization:** Consented patients will be randomized using a computer-generated algorithm to the control group (1-2 mL of intravenous saline every 6 hours for 5 days after admission) or treatment group (15 mg of intravenous ketorolac every 6 hours for 5 days after admission).
- Treatment:** Ketorolac (15 mg) has been chosen as the treatment of choice for several reasons:
 - Ketorolac has a similar pharmacodynamics profile as indomethacin, which was used

in our previous animal model (Xiang et al., 2012).

(2) It is readily available intravenously obviating limitations of oral intake.

(3) In numerous prospective clinical studies, ketorolac infusion produced no change in cardiac or hemodynamic parameters in patients undergoing major vascular surgery (Camu, Van Overberge, Bullingham, & Lloyd, 1990; Peirce, Fragen, & Pemberton, 1990).

(4) 30 mg is the approved dose that is consistent with United States Food and Drug Administration (FDA) labeling per the package

(5) Ketorolac is part of the routine trauma acute pain protocol

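### The Aim 1 Poisson regression of length of stay and complications on cytokines and NISS makes no provision for dispersion, and its default variance does not fit the plan's own SD

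*Combined protocol and SAP*

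**What the plan says.** The Aim 1 text of the IRB application (Research Description, Research Procedures) lists "Outcome variables (hospital and ICU length of stay and occurrence of pneumonia and/or ARDS and/or SIRS or death" as outcomes. It says that these and "the predictor variables of interest (inflammatory markers and NISS) will be compared using Poisson regression". The next sentence gives multiple logistic regression for the odds of post-traumatic complications. The one after that covers adjustment: "The covariates will be adjusted for in the regression models: age, sex, injury severity", followed by head or extremity severity, mechanism and injury outcome. Nothing is said about a scale parameter, a dispersion check or robust standard errors.

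The protocol treats hospital stay separately. Section 3 has "Primary Outcome: Length of Hospital Stay". Section 6 sizes the trial "Using a significance level of 0.05 and an assumed SD of 1.5 days". Section 7 states: "An analysis of variance model will be fit to compare log-transformed LOS between the 2 groups". It summarises LOS by medians and interquartile ranges. Section 7 contains no model relating cytokines or NISS to LOS or to complications, so the Aim 1 text is the only specification of that analysis.

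**The concern.** A Poisson model with default standard errors takes the variance of the outcome, given the covariates, to be equal to its mean. If the true residual variance is smaller, standard errors are too large and real associations are missed. If it is larger, standard errors are too small and false associations are reported. The coefficients themselves are not the issue; their confidence intervals and p-values are.

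What is at stake is the evidence linking cytokines and NISS to LOS and complications. This matters to the trial's rationale, because the Background sections present prediction of LOS by cytokines added to NISS as a preliminary finding of the group. The randomised comparison of LOS is not at stake.

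**Working it through.** **Inputs**
- SD of hospital LOS: 1.5 days, so variance 2.25 (Section 6).
- Difference 0.928 days, 42 per group, 80% power, significance level 0.05, dropout up to 25%, enrolment 112 (Section 6).
- Mean LOS: not stated. Section 10 enrols patients "with anticipated admission of ≥ 5 days (to ensure completion of the treatment"). That is an eligibility expectation, not a mean. I assume 5 to 10 days and show the range.
- ICU stay: no mean, SD or proportion admitted is given.
- Complication rate: not stated. I assume 30% for illustration.

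**The plan's own figure.** Two-sided, n per group = 2 × (1.96 + 0.842)² × 2.25 / 0.928² = 41.01, rounded up to 42. Power from the noncentral t at 42 per group is 80.0%. 84 / (1 − 0.25) = 112. The sample size reproduces, so an SD of 1.5 is what the plan relies on.

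**Hospital LOS with the plan's SD.** Dispersion = SD² / mean. Ratio of default to true standard error = √mean / SD. Actual size of a nominal 5% test = 2 × [1 − Φ(1.96 × ratio)].

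| Assumed mean (days) | Dispersion | SE ratio | Actual size |
|---|---|---|---|
| 2.25 | 1.00 | 1.00 | 5% |
| 5 | 0.45 | 1.49 | 0.35% |
| 7 | 0.32 | 1.76 | 0.05% |
| 8 | 0.28 | 1.89 | 0.02% |
| 10 | 0.23 | 2.11 | below 0.01% |

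The Poisson assumption agrees with the plan's SD only at a mean of 2.25 days. Covariates that explain part of the variance reduce the residual variance below 2.25 and widen the gap.

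**What that costs.** As an illustration only, take a two-group contrast of 0.928 days with 42 per group (this is not the Aim 1 model). With default Poisson standard errors, approximate power is 46%, 27% and 10% at means of 5, 7 and 10. In a simulation with gamma-distributed stays rounded to whole days and 2000 runs per setting, it was 51%, 32% and 12%. Robust standard errors gave 79% to 81%, with type I error of 5.5% to 6.7%.

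**The other direction.** The error turns anti-conservative once the residual SD exceeds √mean: 2.24 days at a mean of 5, 3.16 at a mean of 10. The log transform and medians in Section 7 suggest that right skew is thought possible. Suppose a mean of 8 and SD of 4 (variance 16; both assumed):
- no variance explained: ratio √8 / 4 = 0.71, size about 17%;
- 30% explained: residual variance 11.2, size about 10%;
- 50% explained: residual variance 8, size exactly 5%.

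The plan gives no SD from which to choose among these.

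**Yes/no outcomes.** A 0/1 event has variance p(1 − p), while Poisson uses p. Default standard errors are therefore too large by 1/√(1 − p). At p = 0.30 this is 1/√0.70 = 1.20, and a nominal 5% test runs at about 1.9%.

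**The case against.** The strongest reply is that the application's Aim 1 text is a summary. It refers the reader to the protocol for the full design, and it differs from the protocol elsewhere (200 patients against 112; t-tests for cytokines against linear mixed models). On this reading Section 7 governs. That stands for the treatment comparison. It does not settle the marker and NISS analysis, which Section 7 neither restates nor withdraws.

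Other parts of the reply also stand:
- A reader might infer that the primary p-value is compromised. It is not: the log-LOS analysis of variance makes no Poisson assumption.
- A reader might infer that the tests are wrong whatever the SD. They are not: they are calibrated when the residual SD equals √mean.
- A reader might infer heavy false-positive rates from skewed stays. Such figures rest on SDs the plan does not give, and they shrink with the variance that covariates explain.
- A reader might infer that ICU days are certainly overdispersed because many are zero. Poisson allows zeros, and no ICU figures are given. The SD of 1.5 days applies to hospital stay only.
- Use of default standard errors is inferred from silence. A scaled or robust variance, if intended, would remove the problem.
- For complications the next sentence already names logistic regression. Only death is not clearly covered.

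**Conclusion.** The concern holds for a secondary association analysis. As written, Aim 1 leaves the Poisson variance at its default, and for hospital LOS that default does not fit the plan's SD at any mean near the 5-day eligibility expectation. On that SD the error is conservative: standard errors about 1.5 to 2.1 times too large at an assumed mean of 5 to 10 days, a real test size of 0.35% or less, and a loss of power. An anti-conservative error is possible if stays are more variable than Section 6 assumes, but its size cannot be derived from the documents. For yes/no outcomes the inflation is 1.20 at an assumed 30% event rate. For ICU days no direction can be shown.

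The conclusion rests on the unstated mean LOS and on reading the silence about dispersion as default practice.

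**What to change.** Amend the Aim 1 sentence, and carry the analysis into Section 7 so that the two agree:
- **Hospital LOS:** use the log-LOS linear model already chosen in Section 7, or keep Poisson with robust (sandwich) standard errors. These handle variance below or above the mean. A negative binomial model alone would not do, because it cannot represent the underdispersion that an SD of 1.5 days implies.
- **ICU days:** Poisson with robust standard errors.
- **Complications and death:** drop Poisson and use the logistic regression already named, stating that it covers death.

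The cost is one sentence and one procedure option, with no new data. The downside is slightly less exact test size in small samples: 5.5% to 6.7% for a nominal 5% in the simulation above, at 42 per group.

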Our preliminary data has shown: (1) elevated blood cytokine concentrations during the acute phase of trauma are correlated with the development of fatal post-traumatic complications [8], (2) that early administration of a non-steroidal anti-inflammatory drug (NSAID) resulted in decreased blood serum levels of IL-6, Prostaglandin E2 (PGE2), improved pulmonary edema, and enhanced arterioles ability to vasoconstrict in response to hemorrhage in animal models [9], and (3) that the addition of the internal physiologic parameters (inflammatory cytokines) to New Injury Severity Score (NISS – a marker of the external anatomical insult) significantly improves the ability to predict hospital length of stay of trauma patients when compared to NISS alone [10]. Our group is the first to use an integrative approach that combines the external anatomic injury data with the internal physiologic response for accurate prediction of patient's clinical outcome. Therefore, if we apply this same mindset to treatment, we can improve the trauma patients' care by addressing both parameters as opposed to solely focusing on the external injury as done in the past. Our ability to modify post-traumatic physiologic response via short-term administration of a NSAID may lead to improved patient outcome.

Over the last decade, clinicians remain puzzled over the safety of NSAID administration after fracture in terms of bone union [11-15]. In addition, given the current landscape for opioid epidemic in the United States [16, 17], alternative non-opioid pain management during acute trauma has the potential to reduce opioid consumption and represents a pivotal component of multimodal analgesia strategy.

Objectives

List your research objectives. Please include a summary of intended research objectives in the box below.

Aim 1: Determine if a brief and low dose scheduled administration of an NSAID (Ketorolac) will reduce the inflammatory cascade and improve the clinical outcomes of orthopaedic trauma patients. Ketorolac will be used as the NSAID of choice because it is of low cost to patients, readily available intravenously, has few side effects, and also decrease opioid consumption in acute trauma [18-21].

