Aim 2: Determine whether patients who received Ketorolac treatment require less opioid medication throughout their hospital and post-operative course. The outcome variable will be patient's subjective pain scores, morphine milligram equivalent intake along with other pain modulating medication intake. Inpatient and outpatient subjective pain reports will be collected and analyzed for pain relief and medication use.

Study Design

Describe and explain the study design (e.g., observational, secondary analysis, single/double blind, parallel, crossover, deception, etc.).

- *Clinical Research:* Indicate whether subjects will be randomized and whether subjects will receive any placebo.
- *Community-Based Participatory Research:* If you are conducting [community-based participatory research \(CBPR\)](#), describe strategies for involvement of community members in the design and implementation of the study, and dissemination of results from the study.
- *Qualitative research:* Indicate ranges where flexibility is needed, if a fixed interview transcript is not available, describe interview topics including the most sensitive potential questions.
- *Research Repositories:* If the purpose of this submission is to establish a Research Repository (bank, registry) and the material you plan to collect is already available from a commercial supplier, clinical lab, or established IRB approved research repository, provide scientific justification for establishing an additional repository collecting duplicate material. Describe the repository design and operating procedures. For relevant information to include, see the [UK Research Biospecimen Bank Guidance](#) or the [UK Research Registry Guidance](#).

This study is a double blinded, randomized, prospective, and multi-specialty collaborative clinical trial to assess the effect of early administration of Ketorolac as a preventative treatment for the post-traumatic complications associated with the hyperinflammatory response in trauma patients. The second objective is to determine whether patients randomized to ketorolac treatment require less opioid analgesics during their hospital and postoperative course than the standard of care (SOC). Please see protocol for full description of study design.

Attachments

Subject Recruitment Methods & Advertising

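### The only analyses that name complications and death as outcomes model markers and injury severity, not randomised arm, so the plan should name a between-arm comparison for these outcomes

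*Combined protocol and SAP*

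**What the plan says.** The IRB application (Research Description, Study Design) gives the purpose as "to assess the effect of early administration of Ketorolac as a preventative treatment for the post-traumatic complications associated with the hyperinflammatory response in trauma patients". Aim 1 under Objectives asks whether ketorolac "will reduce the inflammatory cascade and improve the clinical outcomes of orthopaedic trauma patients". Protocol Section 3 makes length of stay primary and lists mortality and "Incidence of Post-Traumatic Complications (e.g., bacterial pneumonia, SIRS, MODS, ARDS, and AKI" among the secondary outcomes.

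Two regressions, both in the application under Research Procedures, Aim 1, name these events as outcomes:

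- **Poisson.** Its outcomes are time in hospital and in the ICU, together with pneumonia, ARDS, SIRS or death. On the other side of the model, "the predictor variables of interest (inflammatory markers and NISS) will be compared using Poisson regression".
- **Logistic.** This model is described in one sentence: "The odds of developing post traumatic complications in the different predictor groups will be determined using multiple logistic regressions".

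The listed covariates are age, sex, injury severity, head and extremity severity, mechanism and *injury outcome*. Randomised arm is neither a predictor nor a covariate.

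Protocol Section 7 names between-arm models for four things: LOS ("An analysis of variance model will be fit to compare log-transformed LOS between the 2 groups"), VAS pain, MME and the cytokines. Its opening sentence also provides t-tests and Fisher exact tests between the two groups for demographic and clinical variables. It names neither complications nor mortality.

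**The concern.** A regression of complications on markers and NISS has as its null that the marker, or NISS, is unrelated to the outcome. That is a prognostic question. The application's Background and protocol Section 4 already report that cytokines correlate with fatal complications, so a positive answer is likely whether or not ketorolac does anything. A real reduction in complications would not appear in these models as a treatment effect.

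At stake is how the trial reports on the objective in its own design statement. If these regressions were presented as the complications analysis, a significant marker coefficient could be taken as evidence about the drug. The comparison that randomisation protects would depend on a general sentence that does not mention the outcome.

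**Working it through.** **1. The plan's own arithmetic.** Section 6 concerns LOS only: n per arm = 2 × (1.960 + 0.842)² × 1.5² / 0.928² = 41.01, rounded up to 42. Exact t power at 42 is 0.800. Allowing 25% dropout, 84 / 0.75 = 112. The stated figures reproduce. No rate, effect or power is given for complications.

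**2. Where the arms are compared.**

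| Outcome | IRB application | Protocol Section 7 |
|---|---|---|
| Cytokines | by arm, t-tests | by arm, mixed models |
| Pain, MME | by arm, t-tests | by arm, mixed models |
| Fracture union | between the two groups | not named |
| LOS | on markers and NISS, Poisson | by arm, ANOVA of log LOS |
| Complications, death | on markers and NISS, Poisson and logistic | not named; general Fisher sentence only |

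The logistic sentence's reference to predictor groups follows directly after markers and NISS are set out as the predictors. Nothing there equates those groups with the randomised arms.

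**3. The covariate.** The Aim 1 paragraph uses *injury outcomes* for bacterial pneumonia, ARDS, SIRS and MODS, then lists *injury outcome* among the adjustment variables. As written, complications are adjusted for themselves.

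**4. Does the marker test carry information on ketorolac?** The documents give no rates or odds ratios, so these are assumptions. I simulated 2,000 trials per setting at 56 per arm. Baseline risk was about 30%, with one marker correlated 0.5 with severity. The fitted model was a logistic regression on marker and severity without arm, set beside a Fisher test by arm.

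| Setting | Marker term p < 0.05 | Fisher by arm p < 0.05 |
|---|---|---|
| No ketorolac effect, marker OR 1.5 per SD | 38% | 4% |
| No ketorolac effect, marker OR 2 | 78% | 3% |
| No ketorolac effect, marker OR 3 | 98% | 3% |
| Ketorolac OR 0.3, marker unrelated | 5% | 61% |

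In the last row, control odds are 0.30/0.70 = 0.429. Times 0.3 this is 0.129, a risk of 11.4% against 30%. The first three marker rates are power for an association that was built in, not false positives. Read with the last row, they show that the marker result follows the marker association and says nothing about the drug.

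**5. Would adding arm be enough?** It depends on which marker enters. With risks of 20–30%, 56 per arm and an effect acting wholly through the marker, an arm comparison with 27–39% power fell to about 4–5% once a post-dose marker was a covariate. The application does not say which day's marker is used. Protocol Section 10(e) takes the first sample before the first dose, and that value could be adjusted for without this loss.

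**6. Precision of a comparison by arm.** Take an assumed control risk p₁, halved to p₂, with n = 56 per arm. Power = Φ{[(p₁ − p₂) − 1.96 × SE₀] / SE₁}, where SE₀ uses the pooled risk and SE₁ the separate risks.

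- 30% to 15%: SE₀ = 0.0789, SE₁ = 0.0776; power 48%; CI half-width 1.96 × 0.0776 = 15 points.
- 20% to 10%: SE₀ = 0.0675, SE₁ = 0.0668; power 32%; CI half-width 1.96 × 0.0668 = 13 points.

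For 80% power about 121 and 199 per arm would be needed.

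**The case against.** The strongest reply is that Section 7 already contains the test. Complications and death are categorical clinical variables, the Fisher sentence is inferential and not limited to baseline, and Section 14 anticipates intention to treat. This largely stands. A reader might infer that complications will never be compared by arm, or that the trial cannot show a ketorolac effect on them. The documents do not support either: the inability belongs to the Aim 1 regressions, not to every test the plan allows. What remains is that the sentence names neither outcome and provides no effect estimate, interval or adjustment.

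Second, the regressions stand in the application, which refers to the protocol for the full design. The protocol has its own analysis plan and target (112 patients, not 200) and contains neither regression. That is fair, but the two texts then disagree, and the protocol does not supply a named replacement.

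Third, the regressions may be meant as prognostic work, in line with the preliminary data on adding markers to NISS. That is plausible, and it means the defect is partly one of labelling.

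Fourth, a reader might set the 38–98% rejection rates against a nominal 5% and call the analysis anti-conservative. That would be wrong: the null being tested is false in those settings.

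**Conclusion.** The concern holds in limited form. The trial's stated objective and two of its secondary outcomes have no named between-arm analysis. The models that do name them omit arm and, as written, adjust for the outcome. They estimate prognostic associations, whichever way they come out.

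This conclusion comes from reading the text and does not depend on the simulation. The simulated rates illustrate it under assumed risks, odds ratios and a single marker. They do not reproduce the full Aim 1 model, which has four markers over five days and more covariates.

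The primary LOS comparison is made by arm and is not affected, so a reader should not extend this point to the main result.

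**What to change.** In Section 7, with Aim 1 of the application made to match:

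- **Main comparison.** Compare the Aim 1 composite (pneumonia, ARDS, SIRS or death) between randomised arms by intention to treat, as a risk difference with 95% CI and a Fisher exact test.
- **Components.** Tabulate each complication and mortality by arm in the same way, but report them descriptively without a claim of significance. This also covers MODS and AKI, which Section 3 lists but the composite leaves out.
- **Supporting model.** Fit a logistic model for the composite with arm and admission NISS, and no post-dose marker. A pre-dose marker would be acceptable.
- **Existing regressions.** Remove injury outcome from the covariates. Label the marker and NISS models as exploratory prognostic analyses that do not test ketorolac.

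The cost is a few sentences and one table from data already being collected. The application's review comments describe enrolment as closed, so the change should be dated and made before these outcomes are analysed by arm. The drawback is imprecision: with intervals of roughly ±13 to ±15 points under the assumptions above, a non-significant result would not show absence of effect.
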